Dependent variables. There are two dependent variables in this study: overall trunk movement (vector magnitude and weight shift count) measured through a single tri-axial accelerometer and self-efficacy for performing weight shifts to prevent pressure ulcers measured with four items on a self-efficacy assessment written specifically for this study.

1. Trunk movement. Trunk movement will be measured using a single tri-axial accelerometer attached to the participant's sternum with a chest strap. The accelerometer used in this study is the Actigraph GT3X+ (Culiolo & Shaw, 2016). The GT3X+ measures accelerations within a dynamic range of +/- 6 units of gravity (G) in three planes of trunk motion, the vertical, anteroposterior, and mediolateral. The accelerometer will be worn throughout the study while the individual is in their wheelchair and taken off at night when sleeping. Trunk movement will be reported in two ways: vector magnitude for counting total movements of the trunk and counts of specific weight shift movement magnitudes based on offset angles of the accelerometer measures. Frequency of data collection will be 30Hz. When measuring continuously for 24 hours/day at 30Hz, the published battery life is 22.5 days and memory limit is 42.5 days. This will require that the participants charge the battery midway through the study. A more detailed description of the specific variables follows.

a. Vector magnitude. A total count of trunk movements in the form of vector magnitude will be averaged across each phase for each participant. The Actigraph GT3X+ provides raw values in each of the three axes. A composite vector magnitude of these three axes (VM) in a specific period of time is a "count" of movement. VM is the square root of the sum of each axis squared. VM will be calculated per second of wear time. For each of the 7 days in a phase, there will be a total VM, which will be graphically portrayed by day for visual analysis of trends for movement within each phase. The overall VM for each phase will be the average VM across the 7 days. This average VM per phase (A1, B1, A2, B2) will be used as the dependent variable for overall trunk movement.

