To determine wear time, two approaches will be used. First, the participants will be asked to document time up to chair and out of chair each day on a daily log (Appendix C). Second, raw accelerometer data will be analyzed for a specific change in orientation based on offset angles and lack of accelerations for a time period of 15 minutes. By asking participants to invert the device on the table, and because this position would be difficult for the device to be in while worn on the chest, it allows for easier detection of the non-wear periods. When there is a question about wear time, the daily logs will be compared with the raw data.

b. **Weight shift count.** Trunk angle offsets from upright will be derived from the raw accelerations. When starting from an upright orientation, an offset angle will be measured in both the anteroposterior and in the mediolateral planes. To determine each participant's trunk angles while performing the prescribed weight shifts, the accelerometer will record while each participant performs a specific sequence of the weight shift maneuvers. From the initial recordings, an algorithm will be adapted for each participant to detect weight shifts in the field-collected accelerometer data. Movements reaching the defined threshold for partial and full weight shifts will be counted. A total count per day and an average count per phase will be recorded. The total daily count, when graphed, can be visually analyzed for trends during each phase. The average phase counts can be compared across control versus intervention conditions.

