Subject ID, subject code or any other person-specific unique identifying number, characteristic or code that can link the subject to their medical data	X	
Dates: All elements of dates [month, day, and year] directly related to an individual, their birth date, date of death, date of diagnosis, etc. Note: Recording a year only is not a unique identifier.	X	
Social Security number		
Medical device identifiers and serial numbers		
Biometric identifiers, including finger and voice prints, full face photographic images and any comparable images		
Web Universal Resource Locators (URLs), Internet Protocol (IP) address numbers, email address		
Street address, city, county, precinct, zip code, and their equivalent geocodes		
Phone or fax numbers	X	
Account, member, certificate or professional license numbers, health beneficiary numbers		
Vehicle identifiers and serial numbers, including license plate numbers		

Check 'None' when none of the identifiers listed above will be recorded, maintained, or shared during the conduct of this study. (exempt category 4)	 None	 None
---	-------------------------------	--

Data Analysis

Power analyses and study endpoints are not required for minimal risk research, pilot or feasibility studies.

No statistical information. *If checked, please explain:*

Data Analysis Plan:

Post-processing of the Actigraph data will be completed with custom software in MATLAB (Mathworks, Natick, MA).

The **vector magnitude** for each second of data during wear-times will be classified as a period of activity or inactivity. Additionally, total vector magnitude of movement for each day will be determined by summing the VM of all active wear-times. Then, for each 7-day phase, the daily values will be averaged for a resulting average phase VM. There will be an average phase VM for each phase A1, B1, A2, and B2.

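### As written, vector magnitude keeps about 1 g of gravity in every second and is summed without dividing by wear time, so the Hypothesis 2 outcome mainly counts seconds and loses movement intensity

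*Combined protocol and SAP*

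**What the plan says.** Hypothesis 2 concerns overall trunk movement, measured as VM. Three parts of the combined protocol and SAP define it.

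- **Dependent variables, 1 and 1a (Vector magnitude).** On the signal: "The Actigraph GT3X+ provides raw values in each of the three axes". On the sampling rate: "Frequency of data collection will be 30Hz". On the formula: "VM is the square root of the sum of each axis squared. VM will be calculated per second of wear time". On the label: "A composite vector magnitude of these three axes (VM) in a specific period of time is a 'count' of movement". Each day then has a total VM, and the phase value is the mean over 7 days.
- **Dependent variables, 1b (Weight shift count).** "Trunk angle offsets from upright will be derived from the raw accelerations".
- **Data Analysis Plan.** VM "for each second of data during wear-times will be classified as a period of activity or inactivity", and then "total vector magnitude of movement for each day will be determined by summing the VM of all active wear-times". The daily values are averaged over the 7-day phase and analysed by linear mixed effects regression.

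None of these places describes subtracting gravity, filtering the axes, or using a named count algorithm. None says how 30 samples become one value per second, gives the threshold for an active second, or divides the daily total by wear time. The mixed model is given no wear-time term.

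**The concern.** An accelerometer at rest registers gravity, and the norm of the three axes of a still device is 1 g whichever way it is tilted. The plan's own use of the raw signal to find static trunk angles works only if gravity is present in it. A norm of those raw values is therefore a large constant with a small movement component added, and a daily sum of it is governed mainly by how many seconds are summed.

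The two descriptions of the sum also differ. Section 1a calculates VM over wear time and totals it by day; the Data Analysis Plan totals only active wear-time. With a 1 g constant in every second, these are quite different quantities.

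VM is the whole of Hypothesis 2 and is named beside weight shifts in the primary hypothesis of the Data Analysis Plan, which intends a causal statement about the map and movement. With this definition, a null result could hide a change in how vigorously participants move, and a positive one could partly reflect longer wear.

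**Working it through.** The documents give no VM figure to reproduce, so the check applies the stated formula. Only step 1 is free of assumptions.

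**1. Still device.** At tilt θ, VM = √(cos²θ + sin²θ) = 1.000 g. This holds at 0, 15, 30, 45 and 60 degrees: sitting upright and holding a lean score the same.

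**2. During a lean.** Assumed: 45-degree lean pivoting at the hip, sensor 0.35 to 0.45 m from the pivot, 30 Hz. At 2 s each way, VM runs from about 0.98 to 1.03 g, mean 1.0003 to 1.0004 g. At 1 s each way, it runs from about 0.93 to 1.13 g, mean 1.004 to 1.007 g.

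**3. A rise in intensity over the same seconds.** Assumed: independent Gaussian dynamic acceleration with SD s (in g) on each axis. Only the two axes at right angles to gravity raise the mean norm, so mean VM ≈ 1 + s². A 30% rise replaces s by 1.3s.

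| s (g) | Mean VM before | Mean VM after | Change |
|---|---|---|---|
| 0.02 | 1.000400 | 1.000676 | 0.03% |
| 0.05 | 1.002500 | 1.004225 | 0.17% |
| 0.10 | 1.010000 | 1.016900 | 0.68% |

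Simulation at s = 0.05 g agrees (1.00251 and 1.00424). Taking the norm minus 1 g, with negatives set to 0, the same rise shows as 31% to 34%.

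**4. Daily totals.** Assumed: 6, 10 or 14 h of wear (6 h is the minimum sitting tolerance in the inclusion criteria), 5%, 20% or 40% of seconds active, background movement of 0.05 g in active seconds, and 45-degree leans taking 4 s in all.

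| Change | All wear seconds, gravity in | Active seconds, gravity in | Gravity removed |
|---|---|---|---|
| Intensity doubled, same seconds | 0.01% to 0.10% | 0.23% to 0.25% | 96% to 100% |
| 20 to 40 leans a day | under 0.001% | 0.4% to 6.9% | 0.2% to 4.0% |
| 5% more wear, equally active | 5.0% | 4.7% to 5.0% | 4.8% to 5.0% |

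For the first row, background of 0.05 g shared over three axes adds 0.05²/3 to the mean norm. Doubling it adds (0.10² − 0.05²)/3 = 0.0025 g per active second, about 0.25% of 1 g. In addition, 25% more active seconds raise the active-seconds total by 23% to 25%.

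**5. Wear time.** In an assumed 12-hour day (720 minutes), 10 extra minutes change the all-wear total by 10/720 = 1.4%, and 30 extra minutes by 30/720 = 4.2%. For the active-seconds total these hold only if the added time is as active as the rest. The last row of the table shows that removing gravity leaves this dependence in place.

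**6. The two descriptions.** With gravity in, the ratio of the all-wear total to the active-only total is about the inverse of the active fraction: 1/0.30 = 3.3 to 1/0.10 = 10 if 10% to 30% of seconds are active (assumed).

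**The case against.** The strongest reply is that section 1a is an incomplete description and not an algorithm. It calls VM a count, it omits the reduction from 30 Hz to one second that must exist, and the Data Analysis Plan leaves post-processing to custom MATLAB code. A filtered signal may be intended, and nothing says in terms that gravity is kept. That possibility stands. But if filtered counts are meant, the norm of raw values is the wrong definition and still has to be replaced.

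A second reply also stands. The analysis plan sums active seconds only, so inactive wear adds nothing and moving more often does raise the total. The hypothesis is worded as an increase in frequency, whereas the percentages in step 3 describe a change in intensity alone. A reader might infer that VM cannot detect movement at all. That fits the all-wear total, not the active-seconds total.

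A reader might also infer that a real effect would be swamped by variation in wear. The documents give no wear-time variability, and each phase value averages 7 days, so this is not supported. Nor is gravity the cause of the wear-time dependence: any unnormalised daily sum has it.

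Finally, the phrase about VM per second of wear time might be taken as a rate. Section 1a goes on to a daily total, and the Data Analysis Plan says the values are summed, so it reads as the epoch length and not as a divisor.

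**Conclusion.** The point holds for the definition as written. VM is a norm of raw acceleration carrying about 1 g per second at any tilt. Summed over all wear seconds, it is close to wear seconds times 1 g and nearly insensitive to movement. Summed over active seconds, it is close to active seconds times 1 g: it follows movement duration but loses intensity, with a 30% rise changing mean raw VM by about 0.03% to 0.68%.

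The 1 g constant follows from the formula and the nature of the signal. The percentages rest on the assumed SDs, wear hours, active fractions and lean shapes. The missing wear-time divisor is a separate weakness that persists after gravity is removed, and the disagreement over which seconds are summed needs settling whichever signal is meant.

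It would be wrong to conclude that the whole primary aim fails. Weight shift counts, the outcome for Hypothesis 1, come from offset angles, which need gravity in the signal, and are unaffected.

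**What to change.** In section 1a and the Data Analysis Plan:

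1. State the signal. If raw acceleration, remove gravity before forming VM, for example by taking the norm minus 1 g with negatives set to 0 at each 30 Hz sample, or by high-pass filtering each axis. If filtered device counts are meant, say so and delete the raw-axis formula.
2. State how 30 Hz samples become one value per second, and the threshold for an active second.
3. Use one rule in both places for which seconds enter the daily total. Whether the all-wear or active-only version is primary is the sponsor's choice.
4. Express VM per hour of valid in-chair wear, or include wear time in the mixed model. The daily logs and non-wear detection already planned supply it.

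The options in item 1 need not treat slow leans alike: step 2 shows that the norm stays within about 0.03 g of 1 g during a 2 s lean. The weight-shift sequence recorded for each participant could be used to compare them before the choice is fixed.

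The cost is a few lines of MATLAB and a wording change in two places, with no new data and no added burden on participants. It should be settled before the processing code is final.

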- 1. Access to the mobile seat interface pressure mapping system (IPM) as a visual feedback system.** This mobile IPM system was designed to provide visual information about seat interface pressure distribution to compensate for lack of sensation on the sitting surface. This variable will be toggled on and off between the A and B phases of the study. The participants will have access to the visual feedback while learning how to complete weight shift maneuvers at the initial visit and then again at home during the A phases (weeks 2 and 4). During the B phases (weeks 1 and 3), they will not have access to the visual feedback from the pressure map. The pressure mapping system consists of a commercially available pressure mat by Vista Medical, and a mobile web-application developed by the research team through a CoDE award provided by the Center for Innovation in 2012 to display the pressure map information on a smartphone screen. The pressure mat connects to the smartphone via Wifi. The smartphone accesses the web application via the phone's data plan while connected to

the mat to display the pressure readings to the user on the phone. No information about the individual, except for the research participant ID number is transmitted to the web application. Each research participant will have a unique password associated with their own ID to use when they log into the web application. The web application resides on a Mayo Clinic server.

2. Education about pressure ulcer risk and how to perform weight shift movements.

Structured education for performance weight shift maneuvers and pressure ulcer prevention will occur during the initial visit. The education method used aligns with principles of the social cognitive theory to facilitate learning. The purpose in providing the education is to ensure all of the participants receive uniform instruction in how to perform weight shifts and to facilitate understanding of the importance of completing them as a protective measure against pressure ulcer development. Because each participant will come into the study at varying levels of understanding about pressure ulcer risk and knowledge of how to complete weight shift maneuvers, the education component is critical to ensure all participants are provided with the same information in the same way.

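### Weight shift detection is set up on deliberate shifts only, so extra trunk movement from using the map could be counted as weight shifts in the map weeks

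*Combined protocol and SAP*

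**What the plan says.** **Access to the map** (Independent variables, item 1). Participants have the map at home in weeks 2 and 4. For the other weeks: "During the B phases (weeks 1 and 3), they will not have access to the visual feedback from the pressure map". I refer to weeks rather than phase letters throughout.

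**What viewing it takes** (same item). The application was built "to display the pressure map information on a smartphone screen". On connection: "The pressure mat connects to the smartphone via Wifi". On login: "Each research participant will have a unique password associated with their own ID to use when they log into the web application". The Background presents the display as available on demand and meant for use across the ordinary day.

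**Sensor** (Dependent variables, item 1). "Trunk movement will be measured using a single tri-axial accelerometer attached to the participant's sternum with a chest strap".

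**Weight shift count, Hypothesis 1** (item 1b). To find each person's trunk angles, "the accelerometer will record while each participant performs a specific sequence of the weight shift maneuvers". The algorithm is adapted per participant from those recordings, and field movements that attain the partial or full threshold are counted. No handling or reaching task, minimum hold time or false-positive check is described. The two-minute hold appears in the self-efficacy items (item 2), not in the counting rule.

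**Vector magnitude (VM), Hypothesis 2** (Data Analysis Plan). "total vector magnitude of movement for each day will be determined by summing the VM of all active wear-times".

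**Planned conclusion** (Data Analysis Plan, last paragraph). A significant increase would be attributed to the map, and it would be stated that weight shifts rise with access to it.

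**The concern.** A sternum accelerometer records how the trunk moves, not why. Reaching for the phone, connecting it, logging in and bending towards a screen can all tilt the trunk. Everyday leans occur in every week and largely cancel when a person is compared with themselves. Handling done in order to see the map does not cancel, because it comes and goes with the condition under test.

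The detection rule is built from examples of what should be counted. The plan describes no examples of what should not be counted. If handling movements pass the rule, the study could report more pressure-relieving shifts when part of the rise is use of the equipment. That matters because the planned conclusion is specifically about weight shifts as a factor in pressure ulcer risk.

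**Working it through.** The plan gives no power, effect size, SD, baseline shift rate or frequency of map use, so there is no figure of its own to reproduce. The check is a line of reasoning followed by two illustrations on assumed inputs.

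**Step 1: does the within-person contrast remove the error?** For mean daily counts, let μ be true shifts without the map, Δ the true effect of the map, f the false counts from ordinary activity (including ordinary phone use), and h the extra false counts from handling done to see the map.

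- Weeks 2 and 4: μ + Δ + f + h
- Weeks 1 and 3: μ + f
- Difference: Δ + h

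The term f cancels and h does not. Because h is present in both map weeks and absent from both others, the rise from week 1 to 2, the fall from 2 to 3 and the rise from 3 to 4 all contain it. The reversal therefore reproduces the pattern expected of a real effect. A mixed model fitted to the same counts cannot separate Δ from h.

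**Step 2: possible size of h.** The reference rate uses two figures from the documents: one shift per half hour (self-efficacy item on consistency) and 6 hours' sitting (inclusion criteria). This gives 6 × 2 = 12 shifts a day. It is a yardstick, not an observed baseline.

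h = (map checks per day) × (share crossing the threshold). Both inputs are assumptions.

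| Checks per day | 10% cross | 25% cross | 50% cross |
|---|---|---|---|
| 2 | 0.2 (1.7%) | 0.5 (4.2%) | 1.0 (8.3%) |
| 5 | 0.5 (4.2%) | 1.25 (10.4%) | 2.5 (20.8%) |
| 10 | 1.0 (8.3%) | 2.5 (20.8%) | 5.0 (41.7%) |

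Cells are false counts per day; percentages are of 12.

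**Step 3: what this could do to the test.** From the plan: target accrual n = 30 and α = 0.05. Assumed: a two-sided paired t-test on map weeks minus other weeks (a stand-in for the planned mixed model), Δ = 0, a constant artefact h, and SD the standard deviation of the paired difference. The test statistic is noncentral t with 29 degrees of freedom and noncentrality (h/SD) × √30. For h = 1.25 and SD = 5, h/SD = 0.25 and the noncentrality is 0.25 × 5.477 = 1.37, so the chance of significance is 26.3%.

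| SD (shifts/day) | h = 0.5 | h = 1.25 | h = 2.5 |
|---|---|---|---|
| 3 | 14.3% | 59.7% | 99.3% |
| 5 | 8.3% | 26.3% | 75.4% |
| 8 | 6.3% | 13.1% | 38.0% |

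With h = 0 the chance is 5%. The spread of the table shows that the inputs decide the answer, and the documents supply none of them.

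**Step 4: vector magnitude.** VM adds up all active wear time, so movement made while using the map enters it. Hypothesis 2 concerns overall trunk movement with access. Movement that follows from access is part of that quantity.

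**The case against.** **The handling is partly inferred.** The text mentions connection, login and a smartphone screen. It does not say where the phone is kept or mounted, how often login is repeated, or whether phone and mat stay in place in weeks 1 and 3; only the visual feedback is said to be withdrawn. Participants must be able to use a smartphone, so ordinary phone handling may occur in every week. This stands. A reader might infer that phone handling happens only in map weeks, but the documents do not support that. Only the excess due to the map, h above, is at issue.

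**Nothing shows that handling attains the threshold.** Each threshold comes from the participant's own shifts, and the algorithm's rejection logic is not described either way. This also stands and makes the concern conditional. It is most plausible for partial shifts. It does not dispose of the point, because the plan describes no step that would show whether false counts occur.

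**Hypothesis 2 is not biased.** A reader might infer that both movement hypotheses are distorted. They are not: handling is real trunk movement that results from access. The limit is on wording, since a rise in VM should not be described as more weight shifting.

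**This is an exploratory, minimal-risk study of 30 people.** That is fair, and it argues for a light remedy. The Data Analysis Plan nevertheless draws a causal conclusion about weight shifts.

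**Conclusion.** The concern holds for Hypothesis 1 in conditional form. If map-specific handling attains a participant's partial or full threshold, the map effect on weight shift counts is inflated by that amount, and the design cannot reveal it. Under the assumed rates the inflation is 0.2 to 5 counts a day, or about 2% to 42% of the yardstick of 12. It may be near the bottom of that range or absent.

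A reader might go further and infer that handling alone would produce a positive trial. The documents do not support this. In the illustration, the chance of significance with no true effect runs from 6.3% to 99.3%, depending wholly on assumed values of h and SD.

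For Hypothesis 2 the conclusion is a caution about interpretation only. Overall this is a cheap improvement to the measurement and not a flaw that invalidates the study.

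**What to change.** **Record a handling block.** At the initial visit, where the map is already used for training and with the sensor worn, record a few minutes of reaching for the phone, connecting, logging in, viewing the map and putting the phone away, with no deliberate weight shift.

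**Use it when setting the rule.** Set each participant's detection rule from this block together with the weight shift sequence, before field data are processed, and apply the same rule to all four weeks.

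**Report its performance.** Give the false-positive rate on the handling block and the sensitivity on the deliberate shifts, separately for partial and full shifts. Do not require that the block give no counts at all, since that may be attainable only by discarding genuine partial shifts.

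**Bound the effect if possible.** If the application stores session times, which the documents do not say, report the Hypothesis 1 contrast with and without those minutes. Present the second result only as a conservative lower bound: it also removes genuine map-guided shifts, and from the map weeks only.

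**Wording.** State that an increase in VM is an increase in trunk movement and will not be described as more weight shifting.

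**Cost.** A few minutes per participant, with equipment already in use. A stricter rule may miss some shallow shifts, and the loss may differ between conditions if the map changes how far people lean. That is why sensitivity should be reported beside the false-positive rate.
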